2.0 Hypothesis

Since complement activation is detectable in animal models of IRI and in human kidneys after IRI, experimental data suggests that use of C1INH prior to induction of IRI shows significant beneficial effects on reducing IRI as well as inflammatory cell infiltrates, and since clinical data from humans indicate significant benefits in reducing dialysis at 1M post-transplant and, more importantly, significant improvements in renal function and graft survival 3.5 years after intravenous C1INH infusion, we hypothesize that the use of C1INH perfused into the kidney prior to transplant in patients receiving deceased donor (DD) kidney transplants with high risk for DGF (KDPI >80) will also show significant reductions in DGF and improved outcomes post-transplant compared with patients receiving KDPI >80 DD transplants receiving placebo treatment.

2.1 Study Objectives

In this study, we propose to investigate the application of pre-operative doses of C1INH (Berinert®) administered by infusion into the renal artery vs.

CONFIDENTIAL C1INH (Berinert®) IRI Study in Kidney Transplant placebo, 1-2 hours prior to implantation, in adult subjects receiving a deceased donor renal allograft considered at high-risk for IRI and DGF (KDPI>80). We hypothesize that C1INH treated patients will demonstrate improved function of the kidney allograft compared to placebo, with equivalence in safety. **The primary objectives of this study are, using a double blinded, placebo controlled format, we will:**

1. Evaluate and compare the safety of C1INH (500U/kidney) administered pre-transplant by surgeons in the operating room in recipients of KDPI >80 kidney allografts from high risk deceased donors.

The secondary objectives are to:

1. Determine if Berinert® (C1INH) study dose 500U/kidney results in benefits of reducing need for dialysis in the 1st month post-transplant.
2. Determine if Berinert® (C1INH) study dose 500U/kidney results in benefits in improving long-term patient & graft survival and results in improved kidney function at 1 year compared to placebo infusions in the kidney.

2.2 Study Synopsis

TITLE	A Phase I/II, Double-Blind, Placebo-Controlled Study: Assessing Safety and Efficacy of Intraoperative Intrarenal Infused C1 Inhibitor(Human) (C1INH) vs. Placebo in Recipients of a Kidney Allograft from Deceased High Risk Donor (KDPI >80) and its impact on Risk for Delayed Graft Function (DGF)
INVESTIGATIONAL AGENT	C1INH (Berinert® [human] [C1INH])
HYPOTHESIS	Pre-operative, infusion of C1INH into the renal allograft artery 1-2 hours prior to implantation will improve early graft function and reduce the rate of DGF, requirements for dialysis, graft survival and eGFR in patients receiving kidney allografts from high risk deceased donor compared to placebo.
RATIONALE	Early graft function has a long-term effect on graft survival. Poor early graft function and DGF contributes to decreased short- and long-term patient and graft survival, increased incidence of acute rejection, prolonged hospitalization, and higher costs of transplantation. Although multiple factors contribute to the impaired graft function, ischemia-reperfusion injury (IRI) is the underlying pathophysiology leading to poor early graft function and DGF. A >35% incidence of DGF has remained constant over time despite significant improvements in immunosuppressive strategies and patient management. This may be due to increased use of kidneys from "extended-criteria" and/or non-heart-beating donors, where even greater rates (>60%) of DGF have been reported.

	
More than 94,653 people are currently waiting for a kidney transplant in the United States (UNOS.org 9/30/2019). Of the 19,360 kidney transplants performed in the US in 2018, 20% were from DCD donors and 9% from donors of KDPI>85. The USRDS reports that more than 50% of patients on the waiting list are willing to accept a kidney from an expanded-criteria donor (KDPI >85). This study will seek to expand the use of high KDPI kidneys and reduce wastage by showing improved function after C1INH treatment.

NUMBER OF PATIENTS AND CENTERS	
40 patients will be enrolled into the study (20 C1INH and 20 Placebo). The study will be performed at Cedars-Sinai Medical Center. In 2018, we transplanted 38 kidneys into patients with KDPI > 85%. We anticipate the rate of offers from OneLegacy will continue at that rate. However, we would propose that 18-20 months will be required to complete study entry given the vagaries of acceptable offers and willingness of individual patients to participate in clinical trials.

INVESTIGATOR / CLINICAL TRIAL LOCATION	
[name]. Cedars-Sinai Medical Center

STUDY OBJECTIVES	
 • To evaluate and compare the safety of Berinert® (C1INH) 500U/kidney in recipients of a kidney allograft from high KDPI donors (KDPI >80) receiving kidneys infused with Berinert® (C1INH) 500U/kidney or placebo pre-operatively. • To evaluate early kidney function in recipients of a kidney allograft from a high KDPI donors following the intra-renal administration of Berinert® (C1INH) pre-operatively compared to placebo.
STUDY DESIGN	
Patients who fulfill all I/E criteria will be eligible to be enrolled into Study
 
I Study Group (40 patients):
 
Treatment Arm I – KDPI >80 kidneys will be infused with one intrarenal dose of 500U of Berinert® in OR prior to implantation into the recipient.
 
Control Arm – KDPI >80 kidneys will be administered one intrarenal dose of normal saline (NS) in the OR in a volume identical to the volume of the dose of Berinert® before implantation of kidney into the patient.
 
Drug v. placebo administration will be randomized 1:1. Drug preparation and randomization will be carried out in a blinded fashion by research pharmacist.

STUDY POPULATION	
Inclusion Criteria:

1) Adult men or women (18-77 years of age) who are on chronic dialysis therapy and acceptable candidates for receipt of a kidney transplant.

2) Recipients who are ABO compatible with donor allograft (A2 to B offers allowable)

3) Understand and sign a written informed consent prior to any study specific procedure

4) AND one of the below criteria:

- Recipients of kidney allograft from KDPI >80 donors
- Recipients of kidney allograft from DCD donors
- Recipients of kidney allograft with CIT > 24 hours
- Recipients of kidney allograft from donor on HD/CRRT prior to death/procurement
- Recipients of kidney allograft with donor terminal creatinine SCr ≥ 3.0 mg/dL
- Patient risk a total risk index score of ≥ 3 based on the following:

Table 1. Characteristics	Risk Index
Donor Age (years)	
<40	0
41-49	1
50-54	2
55-59	3
>60	6
Cold Ischemia Time (hours)	
0-12	0
13-18	1
19-24	2
24-30	3
31-36	4
>37	6
Recipient Race	
Non-black	0
Black	1
Recipient with Diabetes	
Has diabetes	1
Donor cause of death due to CVA	
Donor age >50 years	3
Donor Terminal Cr	
TCr >4	3
TCr $\geq 2-4$	2
Tcr <2	0

Exclusion Criteria:

- Patients with a known pro-thrombotic disorder. (eg. Factor V Leiden)
- Patients with a history of thrombosis or hypercoagulable state, excluding access clotting.
- Patients with a history of administration of C1INH containing products or recombinant C1INH within 15 days prior to study entry.
- Patients with a known hypersensitivity to treatment with C1INH.
- Patients with an abnormal coagulation function. (INR >2 , PTT > 50 , PLT $<60,000$) who are not on anti-coagulation.

	
6) Patients with known active presence of malignancies.
 
7) Patients who are PCR positive for Hep B, Hep C, or HIV.
 
8) Recipients of pre-emptive kidney transplantation (unless baseline SCr is ≥ 4 mg/dL, making minimal urine output)
 
9) All zero mismatch kidneys.
 
10) Recipients of multi-organ transplants. (kidney and any other organ)
 
11) Recipients of kidney allograft that was arriving on pump preservation
 
12) Recipients of kidney allograft from a living donor.
 
13) Female subjects who are pregnant or lactating.

STUDY ENDPOINTS	
SAFETY:
 
 Overall incidence of adverse events and serious adverse events and relationship of AE and SAEs to the study treatment Need for HD in the 1st month post-transplant. eGFR at 1M, 3M, 6M Patient and graft survival at Day 180 Rate of acute cellular rejection (ACR) and antibody mediated rejection at 6M 
EFFICACY ASSESSMENTS:
 
Primary Endpoints
 
Need for Dialysis in the 1st Month Post-Transplant: (Excluding patients who get dialysis for hyperkalemia)
 
 The proportion of patients enrolled who require at least one session of dialysis in the first 30 days post transplant. Number of dialysis sessions per patient in the first 30 days post transplant. 
Renal Function and Graft Survival 6M
 
 eGFR at 6M post-transplant Patient & Graft survival 6M post-transplant 
Secondary Endpoints
 
 Rate of acute cellular and antibody mediated rejection episodes by day 180 Calculated creatinine clearance at 1M, days 90, 180days post transplant. Development of DSAs at 6M SOC biopsies will be assessed at time of implantation and 6M post implantation.
IMUNOSUPPRESSION REGIMEN	
 Induction therapy using Thymoglobulin in divided doses (total of 6mg/kg) or Campath 1H 30mg SQ x 1. Calcineurin inhibition (Tacrolimus or Cyclosporine) will be initiated as per standard practice

	
 • MMF will be started per standard of care (SOC). • Corticosteroids will be used per SOC. • Valgancyclovir will be used as the prophylaxis for CMV for a minimum of 6 months. • Prophylaxis for bacterial and fungal infection will be per institutional SOC. • Diagnosis and treatment of acute cellular or antibody-mediated rejection will be per institutional SOC.
STATISTICAL ANALYSIS	Descriptive and comparative statistics will be used to evaluate results
Study Timelines	
Phase 1: Patient Entry. Once the study is approved by CSMC IRB and contracting, we anticipate a study entry period of up to 18-20 months to complete study entry.
 
Phase 2: Follow Up to Study Completion. The next phase of the study will be having each subject complete the study which is 6 months. Depending on our rate of entry, this means the study could last an additional 6 months from completion of patient entry.
 
Phase 3: Data collection, analysis and preparation of manuscript. Once every patient has completed the study, we anticipate an additional 6M to complete data collection, analysis and preparation of abstract presentations and manuscript.
 
Total Study Time: 36-40M (estimated)

3. Investigator(s) And Other Study Participants

Information regarding additional key personnel involved in the conduct of the study, including names and contact details of participating investigators, monitors, clinical laboratories, technical departments, as well as information on members of additional study committees, will be found in the study files of the sponsor and on site if requested.

A Data Safety Monitoring Board (DSMB) committee will review safety data. Quarterly assessment of AEs & SAEs will be performed and reported to FDA and Cedars-Sinai IRB. In addition, DSMB must be informed and may be convened at any time questions about safety arise and/or thromboembolic events occur. Please see appendix E FDA Guidance for Clinical Trial Sponsors.

4. Investigational Plan

4.1 Study Design And Plan

This is a Phase I/II double-blind, randomized, placebo-controlled study assessing safety and limited efficacy of intraoperative C1INH (500U/kidney) vs. Placebo administered into the graft renal artery 1-2 hours prior to implantation in adult subjects receiving a deceased donor kidney allograft considered high-risk for development of DGF (KDPI>80). Once eligible patients are identified, consented, and have an acceptable kidney transplant offer, they will be randomized by the Cedars-Sinai Research Pharmacy to

CONFIDENTIAL

C1INH (Berinert®) IRI Study in Kidney Transplant receive study drug vs. placebo. Drug and placebo will be prepared by the Cedars-Sinai Research Pharmacy and conveyed to the operating room in a blinded manner. The drug will be administered by the transplant surgeon in the OR in a blinded manner.

4.1.1 Study Drug Administration Timing

In consideration of the latest time point of treatment application before graft reperfusion (ie. beginning of renal vein anastomosis), study treatments will be administered pre-operatively, 1-2 hours before graft reperfusion. Due to the biologic half-life of C1INH (approximately 2.5 to 3.8 days), the time difference between early and late intraoperative treatment application, is thought to be negligible; however, we will administer the C1INH or placebo product at 1-2 hours prior to implantation for dosing consistency. This will constitute the entirety of C1INH vs. placebo administration. The study format is shown below in figure 9.

[figure not shown]

Figure 9: Study format to evaluate C1INH in DGF.

4.2 Selection Of Study Population

Persons legally incompetent to provide informed consent include, but may not be limited to, minors (children), individuals who are mentally incapable of understanding the implications of the PI/IC, and those who are physically unable, by any written, physical or verbal means, to confirm their understanding and consent to take part in the study. Our policy is not to

enter adult patients who are mentally incompetent to give informed consent. Exceptions must be approved by the Study Director.

Up to 40 adult men and women (18-77 years of age) who are recipients of a kidney transplant and only a kidney allograft from a deceased donor who is high risk for DGF will be enrolled in the study (KDPI >80).

4.2.1 Inclusion Criteria

Recipient Inclusion Criteria

- 1). Adult men or women (18-77 years of age) who are on chronic dialysis therapy and acceptable candidates for kidney transplant.
- 2). Understand and sign a written informed consent prior to study specific procedures.
- 3). Recipients who are ABO compatible with donor allograft. (A2 to B offers allowable)
- 4). AND one of the below criteria:
 - a) Recipients of kidney allograft from **KDPI >80** donors
 - b) Recipients of kidney allograft from DCD donors
 - c) Recipients of kidney allograft with CIT > 24 hours
 - d) Recipients of kidney allograft from donor on HD/CRRT prior to death/procurement
 - e) Recipients of kidney allograft with donor terminal creatinine SCr ≥ 3.0 mg/dL
- f) Patient risk a total risk index score of ≥ 3 based on the following:

Table 1. Characteristics	Risk Index
Donor Age (years)	
<40	0
41-49	1
50-54	2
55-59	3
>60	6
Cold Ischemia Time (hours)	
0-12	0
13-18	1
19-24	2
24-30	3
31-36	4
>37	6
Recipient Race	
Non-black	0
Black	1
Recipient with Diabetes	
Has diabetes	1
Donor cause of death due to CVA	
Donor age >50 years	3
Donor Terminal Cr	
TCr >4	3
TCr $\geq 2-4$	2
Tcr <2	0

4.2.2 Exclusion Criteria

- 1) Patients with a known pro-thrombotic disorder. (eg. Factor V Leiden)

- 2) Patients with a history of thrombosis or hyper-coagulable state, excluding access clotting.
- 3) Patients with a history of administration of C1INH containing products or recombinant C1INH within 15 days prior to study entry.
- 4) Patients with a known hypersensitivity to treatment with C1INH or blood products.
- 5) Patients with an abnormal coagulation function. (INR ≥ 2 , PTT > 50, PLT < 60,000) who are not on anti-coagulation.
- 6) Patients with known active presence of malignancies.
- 7) Patients who are positive for Hep B, Hep C, or HIV PCR test.
- 8) Recipients of pre-emptive kidney transplantation. (unless baseline SCr is ≥ 4 mg/dL, making minimal urine output)
- 9) All zero mismatch kidneys.
- 10) Recipients of multi-organ transplants. (kidney and any other organ)
- 11) Recipients of kidney allograft that was arriving on pump preservation
- 12) Recipients of kidney allograft from a living donor.
- 13) Female subjects who are pregnant or lactating.

4.3 Removal Of Subjects From Study

A subject who is withdrawn is one who discontinued in the clinical study for any reason. Subjects may be withdrawn from the study for the following reasons:

- At their own request or at the request of their legally acceptable representative.
- If, in the investigator's opinion, continuation in the study would be detrimental to the subject's well-being.
- At the specific request of the sponsor.

In all cases, the reason for withdrawal must be recorded in the case report form and in the subject's medical records.

Patients have the right to withdraw from the study at any time for any reason without penalty or prejudice. The Investigator also has the right to withdraw patients from the study if he/she feels it is in the best interest of the patient or if the patient is uncooperative or non-compliant. It is understood by all concerned that an excessive rate of withdrawals can render the study un-interpretable; therefore, unnecessary withdrawal of patients should be avoided. Should a patient decide to withdraw, all efforts will be made to complete and report the observations, and early withdrawal procedures, as thoroughly as possible.

The Investigator should contact the patient either by telephone or through a personal visit to determine as completely as possible the reason for the withdrawal. A complete final evaluation at the time of the patient's withdrawal should be made with an explanation of why the patient is withdrawing from the study. If the reason for removal of a patient from the study is an adverse event or an abnormal laboratory test result, the principal specific event or test will be recorded on the CRF. For all patients who are withdrawn pre-maturely, every attempt should be made to assess the patient's status (i.e. patient and graft survival, malignancies, etc.) at 30 days after administration of the last dose of study medication.

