4.5.8 Blinding

The investigational drug pharmacist will be contacted by the study staff and informed of a patient's eligibility. The pharmacist will prepare the blinded study medication or placebo. The study treatment will be prepared according to a pharmacist-supplied randomization code (blinded from all other study personnel). The study treatment will be prepared in a non-siliconized sterile syringe (Berinert® {500U} for all individuals) and labeled with:

- Protocol Number
- Screening number
- Randomization number.

The pharmacist will check the non-siliconized IV syringe for potential particulates. If none are found, the blinded syringe of study treatment, labeled as stated above, will be transported to the surgical suite and matched with the matching patient chart. For the placebo arm, an equivalent volume of normal saline will be prepared in an identical dispensing medium as the C1INH product, labeled as stated above, and transported to the surgical suite and matched with the matching patient chart. Before the study treatment (Berinert or placebo), heparinized normal saline will be administered to the allograft. This method of drug administration has not been FDA approved and may have unforeseen risks

In case of a medical emergency, the study drug assignment for a particular patient may be unblinded. Unblinding study drug assignment will only be necessary if knowledge about treatment is needed for the medical management of the patient. The patient's treatment assignment can be identified for unblinding purposes by calling the Investigational Pharmacist [contact]). When this is necessary, the investigator must immediately notify the IRB, and document the reason and date of the un-blinding. The event must also be documented on the study termination record, the AE page of the CRF, and in source documents. Additionally, the Principal Investigator will submit to the IRB a written explanation describing the event within 5 working days. The procedures for un-blinding study drug treatment will be provided to the Principal Investigators prior to study implementation.

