4.5.9 Treatment Compliance

There is only one application of the drug, which takes place approximately 60-120 minutes prior to graft reperfusion administered pre-operatively.

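### Section 4.3 lets the investigator or sponsor end a patient's participation after the only dose has been given, and nothing then requires the Day 90 or Day 180 outcomes

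*Combined protocol and SAP*

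**What the plan says.** Section 4.3 defines withdrawal as leaving the study: "A subject who is withdrawn is one who discontinued in the clinical study for any reason". It gives several routes. Two matter here:

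- The investigator may withdraw a patient in that patient's best interest, "or if the patient is uncooperative or non-compliant".
- The sponsor may have a patient withdrawn: "At the specific request of the sponsor". No reason is needed.

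The section also covers cases where an adverse event or abnormal laboratory result is the reason for removal, and asks for that event or test to be recorded.

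Study treatment is one intrarenal dose. Section 4.5.9 says "There is only one application of the drug", and Section 4.1.1 says "This will constitute the entirety of C1INH vs. placebo administration".

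For patients who leave early, Section 4.3 asks for the reason and for an evaluation on leaving: "A complete final evaluation at the time of the patient's withdrawal should be made". It also asks for an attempt to establish status (patient and graft survival, malignancies and similar) "at 30 days after administration of the last dose of study medication". Section 7.3 requires each SAE to be followed until it resolves or stabilises. The instruction in Section 4.3 to make all efforts to complete observations is worded for a patient who decides to leave, not for one whom the investigator or sponsor removes.

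**The concern.** Non-compliance is a natural ground for stopping a continuing treatment. Here the treatment is complete once the kidney has been infused, so removing a patient afterwards saves no exposure and costs outcome data.

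The data at risk include primary efficacy endpoints: 6-month eGFR and 6-month patient and graft survival (Section 4.6.1.1). Rejection to Day 180, DSA at 6 months (Sections 4.6.1.2 and 4.6.3.5) and adverse events arising after withdrawal (Section 4.6.2.6) are exposed too.

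The loss need not be random. Section 4.3 foresees removal because of an adverse event or abnormal laboratory result, and Section 7.2.6 gives a laboratory abnormality that leads to withdrawal as an example of clinical relevance. In a trial that measures kidney function, rejection and safety, those reasons overlap with the outcomes themselves.

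**Working it through.** **Timeline.** The dose is given on Day 0, so the status check 30 days after the last dose falls at about Day 30. The late endpoints are at Day 180. The gap is 180 − 30 = 150 days, about five months. A patient removed after Day 30 has a final evaluation at that point, but again nothing is required later.

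**Safeguards elsewhere.** Dropouts are not replaced (Section 4.5.7). Section 6.1 has a heading and no text, and the synopsis offers one general line on descriptive and comparative statistics. No analysis set or missing-data rule says how a removed patient is handled. No sample size, power or withdrawal rate is stated, so there is no figure of the plan's own to reproduce.

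**Inputs for size.** 20 patients per arm (Sections 2.2 and 4.5.7), so one patient is 1/20 = 5% of an arm. The event rates and numbers removed below are assumptions, shown as a range.

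**1. Event patients lost from one arm.** Assume 4/20 = 20.0% truly have the event by 6 months in both arms, and that k event patients are removed from one arm and leave its denominator. The observed rate is (4 − k)/(20 − k):

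| k | Observed rate | False difference |
|---|---|---|
| 1 | 3/19 = 15.8% | 4.2 points |
| 2 | 2/18 = 11.1% | 8.9 points |
| 3 | 1/17 = 5.9% | 14.1 points |
| 4 | 0/16 = 0.0% | 20.0 points |

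If these patients instead stayed in the denominator and were counted as event-free, the false difference would be k/20, that is 5, 10, 15 or 20 points. The size does not depend much on the denominator convention.

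**2. The same removal pattern in both arms.** Assume true rates of 8/20 = 40% and 4/20 = 20%, a 20-point difference, and that half of the event patients in each arm are removed. The observed rates are 4/16 = 25.0% and 2/18 = 11.1%, a difference of 13.9 points. Removal that ignores treatment but follows outcome still distorts the comparison.

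**3. Uncertainty from missing outcomes.** With k patients missing per arm, the best-case to worst-case bounds on a risk difference span 2k/20: 10, 20, 30 and 40 points for k = 1, 2, 3 and 4.

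**4. Mean eGFR.** If k removed patients lie d mL/min/1.73 m² below the rest of their arm, the arm mean rises by k × d/20. This runs from 1 × 10/20 = 0.5 to 4 × 30/20 = 6.0.

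**The case against.** The other side has several good points.

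- **Not everything is lost.** A reader might infer that withdrawal only deletes outcomes. It does not: earlier data, the final evaluation, the Day 30 status attempt and follow-up of reported SAEs remain. Section 4.3 also tells investigators to avoid unnecessary withdrawals.
- **Withdrawal can sometimes prevent treatment.** Randomisation precedes the operating room (Section 4.5.3), and a transplant may be cancelled (Section 4.5.7). The point is therefore limited to withdrawal after infusion.
- **Non-compliance can refer to procedures.** Visits and samples continue after Day 0. That is a reason to stop those procedures, not to stop collecting outcomes that medical records can supply.
- **Blinding.** Investigators, patients and sponsor are blinded (Section 4.5.3), which makes deliberate removal by arm unlikely. With equal true rates, a one-arm loss as in step 1 would then be a chance imbalance, not a systematic bias. Blinding does not stop outcome-related removal, as step 2 shows.
- **Unblinding.** Section 4.5.8 says of an emergency unblinding that "The event must also be documented on the study termination record", and a reader might infer that unblinded patients are taken out of the trial. The sentence lists where to document the event, alongside the AE page and source documents. Emergency unblinding is not among the grounds for withdrawal in Section 4.3, so that reading is not supported.
- **Pilot status.** This is a 40-patient feasibility and safety study, stated not to be powered for efficacy. That lowers the stakes for efficacy, but with so few patients each lost outcome counts for more in the description of safety.

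**Conclusion.** The point holds in a limited form. After infusion, Section 4.3 allows the study team to end a patient's participation on grounds that no longer bear on treatment, and no text requires the outcomes that fall after withdrawal and the Day 30 check. Primary 6-month endpoints can be lost, possibly in relation to outcome.

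The size is illustrative: about 4 to 20 points of false difference for 1 to 4 event patients lost from one arm, given true rates of 4/20 in both arms and removed patients leaving the denominator. The documents give no withdrawal rate.

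Two stronger conclusions are tempting and unsupported. First, the documents do not say that non-compliant patients do worse; that is plausible but an assumption. Second, no section says that withdrawn patients are dropped from the analysis; the plan is silent. The change is worth making because it is cheap, not because bias has been shown.

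**What to change.** In Section 4.3, state that after infusion only the patient's own withdrawal of consent ends outcome collection. Non-compliance, investigator judgement and sponsor request should be recorded as reasons for stopping study visits or procedures. For these patients, collection of eGFR, dialysis, patient and graft survival, rejection, DSA and AEs continues to Day 180, from medical records or by telephone if needed. State also that they stay in the analysis as randomised; Section 6.1, now empty, is the natural place for that sentence.

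Section 4.5.8 needs no change on this account. The patient's right to leave, clinical care and the number enrolled are unaffected.

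The cost is a short wording amendment and some chart-review follow-up. Data on these patients will be less complete than from scheduled visits.

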4.5.7 Selection And Timing Of Dose For Each Subject

The active treatment arm (Berinert® 500U/kidney) will be compared to a placebo control treatment arm, with a total of 20 adult subjects in each study group. A total of 40 adult subjects will be enrolled in the study and additional subjects will not be enrolled to replace dropouts. This design is not statistically powered to show differences in DGF; a 30-50% reduction in DGF predicted for the Berinert® study group. Treatment effect will be investigated following renal artery infusion with Berinert® or an equivalent volume of placebo (0.9% normal saline) pre-operatively prior to graft reperfusion. The C1INH or placebo dose will be preceded by an intrarenal administration of heparinized normal saline.

If a patient is enrolled into the study but the transplant does not occur as planned (e.g. transplant is cancelled due to donor organ quality at time of transplant), the patient will be considered a "screening without transplant". The patient will be maintained on the study ID # that was assigned

CONFIDENTIAL

C1INH (Berinert®) IRI Study in Kidney Transplant

at enrollment but will not be followed past the screening day. IF the patient receives another transplant offer (at any time while study enrollment is still open), the patient will be allowed to continue with the study protocol, with Day of Transplant = Day 0, as if the screening and consenting occurred during the current admission.

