4.6 Study Variables

4.6.1 Efficacy Variables

4.6.1.1 Primary Efficacy Endpoints

For patients who require dialysis in the first 30 days: (Excluding patients who get dialysis for hyperkalemia)

- The proportion of patients enrolled who require at least one session of dialysis in the first 30 days post transplant.
- Number of dialysis sessions per patient in the first 30 days post-transplant.

Renal function and graft survival 6M

- **eGFR at 6M post-transplant**
- **Patient and graft survival at 6M post-transplant**

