4.6.2.7 Secondary Safety Endpoints

- Chemistry and coagulation parameters
- eGFR at 1M, 3M, 6M
- Patient survival at day 180
- Graft survival at day 180
- Rate of acute cellular and antibody mediated rejection episodes at day 180
- Rate of de novo Donor Specific Antibody (DSA) development

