4.6.3.5 Days 90, 180 ±30 days

- Concomitant medications
- Physical examination (may occur as a video visit)
- Dialysis assessment
- Vital Signs/weight
- Adverse Event Assessment
- Calculated estimated GFR
- Hematology & chemistry profile
- Urinalysis
- ACR assessment on Day 180
- Assessment of SOC biopsies on Day 180
- Patient survival assessment on day 180
- Graft survival assessment on day 180
- Donor Specific Antibody (DSA) assessment at Day 180

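### The status check after withdrawal falls on Day 30, so 6-month survival need not be ascertained for patients who withdraw before about Day 150 alive with a functioning graft

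*Combined protocol and SAP*

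**What the plan says.** Section 4.3 lets a patient leave at their own wish, on the investigator's judgement, or at the sponsor's request. Three provisions then govern data collection:

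- If the patient chooses to leave, efforts are to be made to complete the observations and early-withdrawal procedures. No date is attached.
- A full final evaluation is to be made when the patient withdraws.
- Every attempt is to be made to establish status ("i.e. patient and graft survival, malignancies, etc.) at 30 days after administration of the last dose of study medication"). This is the only provision tied to a fixed study time.

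The trial has one dose. Section 4.5.9 states: "There is only one application of the drug, which takes place approximately 60-120 minutes prior to graft reperfusion". Section 4.1.1 agrees: "This will constitute the entirety of C1INH vs. placebo administration".

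Section 4.6.1.1 lists "Patient and graft survival at 6M post-transplant" among the primary efficacy endpoints. Section 4.6.2.7 lists patient survival at the same time point and "Graft survival at day 180" as secondary safety endpoints. The visit schedule in 4.6.3.5, with a window of ±30 days, includes "Graft survival assessment on day 180".

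Section 4.5.7 plans 20 patients per arm and says that "additional subjects will not be enrolled to replace dropouts".

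**The concern.** The check is anchored to the last dose, but the endpoint is anchored to the transplant. In this trial both clocks start on Day 0, so the check comes five months before the endpoint it needs to inform. It is a stated rule set at the wrong time for the trial's own endpoint, rather than a detail left unwritten.

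Withdrawal happens after randomisation and need not be random. Section 4.3 allows removal for the patient's well-being, or for poor cooperation or compliance, and either could plausibly go with a failing graft. Deaths and graft losses after the last required contact could then go unrecorded in the patients where they are more likely. The protocol gives no data on this link. With small arms and no replacement, a few unknown outcomes would matter.

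**Working it through.** The plan has no figure of its own to reproduce: section 6.2 says that no sample size was determined, and no withdrawal rate is given anywhere.

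**Inputs.** Last dose on Day 0 (4.1.1, 4.5.9); check 30 days later (4.3); endpoint at Day 180, window ±30 days (4.6.3.5); 20 per arm (4.5.1, 4.5.7).

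**Timing.**

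- Day of the check: 0 + 30 = Day 30.
- Day 180 window: 180 − 30 = Day 150 to 180 + 30 = Day 210.
- From the check to the window opening: 150 − 30 = 120 days. From the check to Day 180: 180 − 30 = 150 days.

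**Last required status, for a patient alive with a functioning graft at that time.** For withdrawal by Day 30 it is the Day 30 check. After that, the check date has passed and it is the final evaluation at withdrawal.

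| Withdrawal | Last required status | Days uncovered to Day 180 | Share of 180 days |
|---|---|---|---|
| Day 10 | Day 30 | 180 − 30 = 150 | 83% |
| Day 60 | Day 60 | 180 − 60 = 120 | 67% |
| Day 100 | Day 100 | 180 − 100 = 80 | 44% |
| Day 150 or later | inside the Day 180 window | endpoint ascertained | none |

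A death known by the last required contact settles the 6-month status, and a known graft loss settles graft survival. The gap is therefore confined to patients who leave before about Day 150 alive with a functioning graft.

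**Size.** Let m be the number of such patients per arm with unknown 6-month status. Counting them all as survivors, then all as failures, gives a range of width m/20 for one arm. For the difference between arms, the extremes pair the best case in one arm with the worst in the other, so the width is 2m/20. The values of m are assumptions.

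| m per arm | Width, one arm | Width, arm difference |
|---|---|---|
| 1 | 1/20 = 5 points | 2/20 = 10 points |
| 2 | 2/20 = 10 points | 4/20 = 20 points |
| 3 | 3/20 = 15 points | 6/20 = 30 points |
| 4 | 4/20 = 20 points | 8/20 = 40 points |

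For scale, the abstract of the earlier intravenous trial in Appendix B reports 7 graft failures among 35 placebo patients and 1 among 35 treated patients over 3.5 years: 20.0% − 2.9% = 17 points. Two unknown patients per arm would give a range wider than that. The earlier trial used a different route and a longer follow-up, so this is only a yardstick.

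**The case against.** A reader might infer that 6-month survival is never ascertained for anyone who withdraws. The documents do not support that. The final evaluation captures late withdrawals inside the visit window and any earlier event already known. The commitment to complete observations permits later collection, and section 7.3 asks that each serious adverse event be followed to resolution or stabilisation, with no stated exception for withdrawn patients. The Day 30 check is a minimum, not a ban on looking later.

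What remains is that none of these requires status at Day 180. The commitment to complete observations is worded for patients who themselves decide to leave, so on its face it does not reach removal by the investigator or sponsor. Following up a known serious event does not establish that a patient with no reported event is alive with a working graft.

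A reader might also infer that the survival comparison would rest on completers only. That does not follow either. Section 6.1 carries no text under its heading, and the synopsis promises only descriptive and comparative statistics. A time-to-event analysis would use withdrawn patients up to last contact. The absence of any analysis or censoring rule is a separate gap.

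The strongest argument on importance is that this is a pilot with safety as its primary objective, stated not to be powered. If 6-month survival were 90% in each arm (assumption), the 95% interval for the difference would be about ±1.96 × √(2 × 0.9 × 0.1/20) = ±19 points, a full width of about 37. One unknown patient per arm adds a range of 10. Sampling error is the larger problem, and this limits the severity. It does not excuse the gap: unknown outcomes can bias the comparison as well as widen it, and these can be avoided cheaply. Withdrawals may also be few, because treatment is complete in the operating room and much of the later measurement is routine care.

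**Conclusion.** The point holds within limits. Section 4.3 sets its dated status check at Day 30, and the protocol does not require 6-month patient and graft survival to be ascertained for patients who withdraw before about Day 150 alive with a functioning graft. Each such patient leaves an arm's 6-month survival uncertain by 5 percentage points, and one per arm widens the bound on the difference by 10.

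These sizes assume that all 20 patients per arm are transplanted and counted, and that status is not obtained by some route the protocol leaves optional. How many patients would be affected is unknown. That withdrawal goes with poor graft outcome is plausible but undocumented. This should be fixed, but it does not by itself invalidate the trial.

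**What to change.** In the last sentence of 4.3, replace the timing relative to the last dose with: *at Day 30 and at Day 180 post-transplant*. Add that vital status, graft status and the dates of any death or graft loss will be obtained from the transplant centre's records for every randomised, transplanted patient, whatever the reason for withdrawal, subject to the patient's consent. On the case report form, record stopping study visits separately from refusing further data collection, so that the first does not end ascertainment of survival.

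The cost is a short amendment and a record check for a few patients at one centre. The consent pages are not among the documents reviewed, so whether the consent form already permits this use of records must be checked. Status will still be missing for patients who refuse it, and the fix does not supply the missing analysis rule for them. With status obtained for all, the widths tabulated above fall to zero.
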